6.2.5.5 Dosage Adjustments for Depression

In severe cases of depression, PEG-IFN should be permanently discontinued and the subject referred for psychiatric intervention.

6.3 FORMULATION, PACKAGING AND LABELING

Pegasys®: 180 µg/mL; 1-mL solution in 2-mL vials

Packaging: TBD

Pegylated Interferon alfa-2a—F. Hoffmann-La Roche Ltd
Protocol YV25718, Version E

83

Storage: Refrigerate at 2°–8°C (36°–46°F)

Study drug packaging will be overseen by the Roche Clinical Trial Supplies Department and bear a label with the identification required by local law, the protocol number, drug identification, and vial contents. The investigator will inform the subject of the dose they are required to take based on their BSA, and this will be recorded in the SMD.

The packaging and labeling of the study medication will be in accordance with Roche standards and local regulations.

The study drug must be stored according to the details on the product label. The drug label indicates the storage temperature.

Local packaging in some countries may be different.

Upon arrival of investigational products at the site, site personnel should check them for damage and verify proper identity, quantity, integrity of seals, and temperature conditions, and report any deviations or product complaints to the monitor upon discovery.

6.4 BLINDING AND UNBLINDING

The study is open label.

6.5 ACCOUNTABILITY OF INVESTIGATIONAL MEDICINAL PRODUCT AND ASSESSMENT OF COMPLIANCE

6.5.1 Accountability of Investigational Medicinal Product

The investigator is responsible for the control of drugs under investigation. Adequate records for the receipt (e.g., Drug Receipt Record) and disposition (e.g., Drug Dispensing Log) of the study drug must be maintained. Accountability will be assessed by maintaining adequate drug dispensing and return records.

Accurate records must be kept for each study drug provided by the Sponsor. These records must contain the following:

- Documentation of drug shipments received from the Sponsor (date received and quantity).
- Disposition of unused study drug not dispensed to subject.

Study drug will be dispensed according to the schedules in [Table 2](#) and [Table 4](#). A Drug Dispensing Log must be kept current and should contain the following information:

- The identification of the subject to whom the study drug was dispensed
- The date(s) and quantity of the study drug dispensed to the subject
- The date(s) and quantity of the study drug returned by the subject

All records and drug supplies must be available for inspection by the Monitor at every monitoring visit.

Subjects will be asked to return all used drug supply containers at each visit and all unused drug supply containers at the end of treatment as a measure of compliance.

When the study is terminated, the investigator will return any used and unused study drug (i.e., empty, partially used, and unused containers) to the Monitor. The completed Drug Dispensing Log and Drug Return Record(s) will be returned to Roche, unless alternate destruction has been authorized by Roche, or required by local or institutional regulations (Section 6.6). The investigator's copy of the Drug Return Record(s) must accurately document the return of all study drug supplies to Roche.

6.5.2 Assessment of Compliance

At each visit, compliance with the study requirements will be reinforced.

Subject compliance with taking study drug as required will be assessed by maintaining adequate study drug dispensing records and review of the SMD. The investigator is responsible for ensuring that dosing is administered in compliance with the protocol. Delegation of this task must be clearly documented and approved by the investigator.

It is mandatory that each injection (date and volume) be recorded in the drug diary and initialed by the person giving the injection (see Section 5.5). Subjects will be asked to return used drug containers at each visit, along with the drug diary. Returned drug containers will be counted and justified against the diary entries by study site personnel. Each verified injection will be recorded on the eCRF at each visit. Unused study drug should be returned at the end of the treatment period (i.e., Week 48). Under no circumstances should the treatment period for any subject extend beyond the allocated 48 weeks.

6.6 DESTRUCTION OF THE INVESTIGATIONAL MEDICINAL PRODUCT/COMPARATOR

Local or institutional regulations may require immediate destruction of used investigational medicinal product (IMP) for safety reasons. In these cases, it may be acceptable for investigational site staff to destroy dispensed IMP before a monitoring inspection provided that source document verification is performed on the remaining inventory and reconciled against the documentation of quantity shipped, dispensed, returned, and destroyed. Written authorization must be obtained from the Sponsor at study start up before destruction.

If there are any issues with the drug, it should be returned to the appropriate Roche clinical trial supplies department for long-term storage and not destroyed.

Written documentation of destruction must contain the following:

- Identity of IMP(s) (and comparators [if applicable]) destroyed
- Quantity of IMP(s) destroyed
- Date of destruction
- Method of destruction
- Name and signature of responsible person who destroyed investigational products(s)

7. SAFETY INSTRUCTIONS AND GUIDANCE

7.1 ADVERSE EVENTS AND LABORATORY ABNORMALITIES

7.1.1 Clinical Adverse Events

According to the ICH, an AE is any untoward medical occurrence in a subject or clinical investigation subject administered a pharmaceutical product and which does not necessarily have a causal relationship with this treatment. An AE can therefore be any unfavorable and unintended sign (including an abnormal laboratory finding), symptom, or disease temporally associated with the use of a medicinal (investigational) product, whether or not considered related to the medicinal (investigational) product. Preexisting conditions that worsen during a study are to be reported as AEs.

7.1.1.1 Intensity

All clinical AEs encountered during the clinical study will be reported on the AE eCRF. **Intensity** of AEs will be graded (mild, moderate, severe) and reported in detail on the eCRF.

Mild	discomfort noticed but no disruption of normal daily activity
Moderate	discomfort sufficient to reduce or affect daily activity
Severe	inability to work or perform normal daily activity

The Division of AIDS Table for Grading the Severity of Adult and Pediatric Adverse Events should be used to assist in the assessment of intensity.

- http://rsc.tech-res.com/Document/safetyandpharmacovigilance/Table_for_Grading_Severity_of_Adult_Pediatric_Adverse_Events.pdf

Note that events that are considered as life threatening should be reported as an SAE (see Section 7.1.1.3) and the intensity would be reported as “severe” on the eCRF.

7.1.1.2 Drug–Adverse Event Relationship

Investigators should use their knowledge of the subject, the circumstances surrounding the event, and an evaluation of any potential alternative causes to determine whether or not an adverse event is considered to be related to the study drug, indicating "yes" or "no" accordingly. The following guidance should be taken into consideration:

- Temporal relationship of event onset to the initiation of study drug

- Course of the event, considering especially the effects of dose reduction, discontinuation of study drug, or reintroduction of study drug (where applicable)
- Known association of the event with the study drug or with similar treatments
- Known association of the event with the disease under study
- Presence of risk factors in the subject or use of concomitant medications known to increase the occurrence of the event
- Presence of non – treatment-related factors that are known to be associated with the occurrence of the event

7.1.1.3 Serious Adverse Events (Immediately Reportable to Roche)

An SAE is any experience that suggests a significant hazard, contraindication, side effect, or precaution. It is any AE that at any dose fulfils at least one of the following criteria:

- Is fatal (results in death**; note: death is an outcome, not an event)
- Is life-threatening (Note: the term “life-threatening” refers to an event in which the subject was at immediate risk of death at the time of the event; it does not refer to an event which could hypothetically have caused a death had it been more severe)
- Requires in-patient hospitalization or prolongation of existing hospitalization
- Results in persistent or significant disability/incapacity
- Is a congenital anomaly/birth defect
- Is medically significant or requires intervention to prevent one or other of the outcomes listed above.

****The term sudden death should be used only when the cause is of a cardiac origin as per standard definition. The terms death and sudden death are clearly distinct and must not be used interchangeably.**

The study will comply with all local regulatory requirements and adhere to the full requirements of the ICH Guideline for Clinical Safety Data Management, Definitions and Standards for Expedited Reporting, Topic E2.

7.1.1.4 Other Safety Findings Requiring Expedited Reporting

Other safety findings may require expedited reporting depending on local legislation, e.g., a major safety finding from a newly completed animal study (such as carcinogenicity).

7.1.2 Treatment and Follow-up of Adverse Events

Subjects experiencing AEs should be treated by accepted clinical procedures. If the use of medications excluded by protocol is deemed necessary, the subject may need to be discontinued from the test regimen after consultation with Roche. All AEs should be followed until resolved or stabilized.

7.1.3 Laboratory Test Abnormalities

Laboratory test results will be recorded on the laboratory results electronic form page ([eForm]) of the eCRF, or appear on electronically produced laboratory reports submitted directly from the central laboratory, if applicable.

Any laboratory result abnormality fulfilling the criteria for an SAE should be reported as such on the AE eForm (see Section 7.2.2).

Any treatment-emergent abnormal laboratory result which is clinically significant, i.e., meeting one or more of the following conditions, should be recorded as a single diagnosis on the AE eForm in the eCRF:

- Is considered an SAE
- Results in discontinuation from study treatment
- Results in a requirement for a change in concomitant therapy (e.g., addition of, interruption of, discontinuation of, or any other change in a concomitant medication, therapy or treatment)

This applies to any protocol and non-protocol-specified safety and efficacy laboratory result from tests performed after the first dose of study drug, which falls outside the laboratory reference range and meets the clinical significance criteria.

This does not apply to any abnormal laboratory result which falls outside the laboratory reference range but which does not meet the clinical significance criteria [these will be analyzed and reported as laboratory abnormalities]; those which are considered AEs of the type explicitly exempted by the protocol; or those which are a result of an AE that has already been reported.

The finding of an elevated ALT or AST ($>3 \times$ baseline value) in combination with either an elevated total bilirubin ($>2 \times$ ULN) or clinical jaundice, in the absence of cholestasis or other causes of hyperbilirubinemia, is considered to be an indicator of severe liver injury. Therefore, investigators must report as an AE the occurrence of either of the following:

- Treatment-emergent ALT or AST $>3 \times$ baseline value in combination with total bilirubin $>2 \times$ ULN (of which 35% is direct bilirubin) or
- Treatment-emergent ALT or AST $>3 \times$ baseline value in combination with clinical jaundice

The most appropriate diagnosis (or if a diagnosis cannot be established, the abnormal laboratory values) should be recorded on the AE eCRF and reported to the Sponsor immediately (i.e., no more than 24 hours after learning of the event), either as an SAE (Section 7.2.2) or a non-serious AE of special interest (Section 7.2.3).

7.1.3.1 Follow-up of Abnormal Laboratory Test Values

Clinically significant laboratory abnormalities should prompt a repeat measure no less frequently than every 2 weeks or as clinically indicated, with appropriate clinical

management, until they return to normal or baseline levels, and/or an adequate explanation of the abnormality is found. If a clear explanation is established it should be recorded on the eCRF. See also Section 6.2.5 for specific guidance.

7.2 HANDLING OF SAFETY PARAMETERS

7.2.1 Reporting of Adverse Events

All AEs (related and unrelated) occurring during the treatment/principal observation period and initial 24 weeks of follow-up must be reported. During the extended long-term follow-up period, only persisting AEs, new-onset SAEs *and* non-serious AEs of special interest related to PEG-IFN, and deaths will be reported.

7.2.2 Reporting of Serious Adverse Events (immediately reportable)

Any clinical AE or abnormal laboratory test value that is serious (as defined in Section 7.1.1.3) and that occurs during the study, regardless of the treatment arm, occurring from the enrollment visit (start of study screening procedures), including extended long-term follow-up must be reported to Roche **within 1 working day** of the investigator becoming aware of the event (expedited reporting).

For initial reports of serious adverse events, investigators should record all case details that can be gathered within 1 working day on the Adverse Event eCRF and submit the report via the Electronic Data Capture (EDC) system. A report will be generated and sent to Roche Safety by the EDC system.

In the event that the EDC system is unavailable, a paper Serious Adverse Event CRF and Fax Cover Page should be completed and faxed immediately to Roche Safety. Once the EDC system is available, all information will need to be entered and submitted via the EDC system.

After informed consent/assent, but prior to initiation of study medications, only SAEs caused by a protocol-mandated intervention will be collected (e.g., SAEs related to invasive procedures such as biopsies, medication washout, or no treatment run-in).

After first study drug, all SAEs must be reported.

Unrelated SAEs must be collected and reported during the study treatment/principal observation period and initial 24 weeks of follow-up.

Related SAEs **must** be collected and reported regardless of the time elapsed from the last study drug administration, even if the study has been closed. *Every effort should be made to follow all SAEs considered to be related to the study drug or study-related procedures until a final outcome can be reported.*

Suspected Unexpected Serious Adverse Reactions (SUSARs) are reported to investigators at each site and associated IRB/IEC when the following conditions occur:

- The event must be an SAE.

- There must be a certain degree of probability that the event is an adverse reaction from the administered drug.
- The adverse reaction must be unexpected, that is to say, not foreseen in the SPC text (Summary of Product Characteristics [for an authorized medicinal product]) or the Investigator's Brochure (for an unauthorized medicinal product).

When all subjects at a particular site are off treatment as defined by the protocol:

- Only individual SUSAR reports originating in that particular trial will be forwarded to the site and associated IRB/IEC on an expedited basis;
- Individual SUSARs considered to be a significant safety issue and/or which result in Roche recommending a change to the Informed Consent Form/assent, will be reported in an expedited manner to all investigators and IRBs/IECs;
- SUSAR reports originating from other trials using the same IMP will be provided as six monthly SUSAR Reports to investigators and IRBs/IECs where long-term follow-up studies are carried out, unless they are considered significant.

This study adheres to the definition and reporting requirements of ICH Guideline for Clinical Safety Data Management, Definitions and Standards for Expedited Reporting, Topic E2. Complete information can be found in [Appendix 3](#).

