3.1 OVERVIEW OF STUDY DESIGN AND DOSING REGIMEN

This is a 2:1 randomized, controlled, parallel-group, open-label, multicenter study of PEG-IFN treatment compared to an untreated control ([Figure 1](#)). Subjects without advanced fibrosis/cirrhosis will be randomized 2:1 to PEG-IFN treatment (Group A) or untreated control (Group B), respectively. Subjects with advanced fibrosis will be assigned to PEG-IFN treatment (Group C). Subjects in Groups A and C will receive PEG-IFN for 48 weeks. The first 48 weeks from randomization will be referred to as the treatment period for Groups A and C and the principal observation period for Group B. The primary endpoint will be assessed 24 weeks after the end of treatment/principal observation period.

Forty-eight weeks after randomization, PEG-IFN will be offered to subjects in the Group B untreated control group who have not experienced HBsAg seroconversion. This offer will be available for up to 1 year following Week 48. If eligible, these subjects will enter the switch arm, where they will receive PEG-IFN for 48 weeks.

The screening period will be up to 35 days. For Group A, Group B non-switch, and Group C subjects the study length is approximately 6 years (1-year treatment/principal observation period and 5 years of follow-up). For Group B switch subjects the study length is up to approximately 8 years (1-year principal observation period, up to 1 year follow-up whilst deciding whether to switch, 1-year switch treatment period, and 5-year follow-up period).

Figure 1 Schematic of Study Design

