8.2.5.3 Safety Data Analysis

The primary safety analysis will compare safety in Group A with Group B *at 24 weeks post-end of treatment/end of untreated observation*. The safety data of Group A and Group B will be qualitatively evaluated alongside subjects in Group C and the switch arm.

- *Incidence, nature, and severity of serious and non-serious AEs (including neurological and psychiatric events)*
- *Reasons for the discontinuation of any study medication*
- *Dose modifications for laboratory abnormalities and clinical AEs*
- *Changes in vital signs and laboratory tests from screening/baseline, including thyroid function*
- *Effect on growth (height and weight)*

The following safety outcome measures will be assessed using descriptive statistics at 1, 2, 3, 4, and 5 years post-end of treatment:

- *Incidence, nature, and severity of persisting AEs, new-onset related SAEs/ non-serious AEs of special interest*
- *Changes in thyroid function from screening/baseline*
- *Effect on growth (height and weight)*

AEs: AEs will be assigned preferred terms and categorized into body systems according to the Medical Dictionary for Regulatory Activities (MedDRA) classification of the World Health Organization (WHO) terminology. Descriptive statistics will be used to summarize safety parameters by group. Neurological and psychiatric AEs will be assessed in further detail, including persistence and duration, as well as new onset of SAEs and non-serious AEs of special interest related to PEG-IFN reported during the extended long-term follow-up period of this study.

Laboratory Safety Data: The laboratory data (including thyroid function) will be analyzed according to Roche's "International Guideline for the Handling and Reporting of Laboratory Data".

Growth (weight and height): The continuous growth will be analyzed with Residual Maximum Likelihood, or analysis of covariance. The assumptions of the analysis such as normally distributed residuals will be assessed. If necessary, rectifying transformations shall be applied. Growth (height) velocity will be explored.

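### Laboratory AEs have no start point for untreated Group B, and the SAE rule contradicts itself, so the A-versus-B AE tables risk uneven recording

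*Protocol*

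**What the plan says.** Protocol 8.2.5.3 sets the comparison at stake: "The primary safety analysis will compare safety in Group A with Group B", at 24 weeks after the end of treatment or of untreated observation.

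**Laboratory AEs.** Protocol 7.1.3 says when an abnormal result goes on the AE form: if it is serious, leads to discontinuation of study treatment, or requires a change in concomitant therapy. The rule covers results "from tests performed after the first dose of study drug, which falls outside the laboratory reference range". A separate paragraph makes an ALT or AST rise above 3 times baseline, with raised bilirubin or clinical jaundice, a mandatory AE, and words it as treatment-emergent. Section 7.2.3 lists that event as one of special interest and refers back to 7.1.3.

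**SAEs.** Protocol 7.2.2 says four things that bear on Group B:
- A serious event is reportable if it "occurs during the study, regardless of the treatment arm, occurring from the enrollment visit".
- After consent but "prior to initiation of study medications, only SAEs caused by a protocol-mandated intervention will be collected".
- Once dosing has begun, the scope is full: "After first study drug, all SAEs must be reported".
- Events judged not to be caused by the drug are tied to a period rather than to dosing: "Unrelated SAEs must be collected and reported during the study treatment/principal observation period and initial 24 weeks of follow-up".

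**All AEs.** Protocol 7.2.1 says: "All AEs (related and unrelated) occurring during the treatment/principal observation period and initial 24 weeks of follow-up must be reported". Under section 3.1, Group B's principal observation period is the 48 weeks that follow its randomization.

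**The concern.** A rule that starts at the first dose has no start in an arm that receives none. Group B is untreated from randomization, and a child in it first meets study drug only on switching, at Week 48 at the earliest. If sites apply the dosing-based wording, the same non-serious laboratory finding becomes an AE in a treated child and only a laboratory value in a control.

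The AE tables would then show a between-group difference made partly by the recording rule. It would run one way, overstating the excess on PEG-IFN, in a trial whose stated purpose is to weigh benefit and risk against no treatment. The special-interest table is the most exposed, because the liver-injury event can arise from the disease itself and the control arm is there to show how often it does.

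**Working it through.** The plan states no AE, SAE or laboratory-event rate, so there is no planned figure to reproduce. The check is a comparison of the rules, followed by an illustration under stated assumptions.

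**Step 1. Which rule reaches an unswitched Group B child?**

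| Type of event | Provisions that cover Group B | Provision tied to dosing | Result |
|---|---|---|---|
| Clinical AE, non-serious | 7.2.1; Table 3 schedules AE collection from baseline | None specific | Covered |
| SAE, including a serious laboratory value | Opening of 7.2.2; unrelated-SAE sentence; 7.2.1 | Two sentences in 7.2.2 | Covered, but contradicted |
| Non-serious laboratory result leading to treatment discontinuation | Not applicable | 7.1.3 | Cannot occur without treatment |
| Non-serious laboratory result changing concomitant therapy | 7.2.1, in general terms only | 7.1.3, first dose | Not clearly covered |
| Non-serious ALT/AST event with bilirubin or jaundice | 7.2.1, in general terms only | 7.1.3, treatment-emergent | Not clearly covered |

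The gap is the last two rows. The contradiction is the second.

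**Step 2. Do the data exist to apply a rule in Group B?** Yes. Protocol Table 3 schedules hematology and chemistry at baseline, Weeks 12, 24, 36 and 48, and follow-up Week 24. What is missing is the instruction that turns a qualifying result into an AE.

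**Step 3. Where would a difference appear?** SAP 4.6.2 tabulates AEs and the special-interest liver events from study beginning to 24 weeks after treatment or observation. SAP 4.1.3 admits Group B to the Safety population without a dose. Group B is therefore in the denominator whether or not its laboratory events were put on the AE form.

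**Step 4. Scale under assumption.** Randomizing 145 in a 2:1 ratio gives 145 × 2/3 ≈ 97 in Group A and 145 × 1/3 ≈ 48 in Group B. Suppose every site follows the literal wording, so that non-serious laboratory AEs are recorded in Group A only. Group A counts are assumed. Fisher's exact test, two-sided:

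| Recorded, A vs B | Group A rate | p |
|---|---|---|
| 5/97 vs 0/48 | 5.2% | 0.17 |
| 7/97 vs 0/48 | 7.2% | 0.10 |
| 8/97 vs 0/48 | 8.2% | 0.053 |
| 10/97 vs 0/48 | 10.3% | 0.031 |
| 15/97 vs 0/48 | 15.5% | 0.003 |
| 10/97 vs 5/48, equal recording | 10.3% (B: 10.4%) | 1.0 |

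The plan tests no AE rates; its AE summaries are descriptive. The p-values only show how large a difference the rule could create if the true rates were equal. They forecast nothing.

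**The case against.** The strongest reply is that Group B is covered several times over. Section 7.2.2 opens with an arm-neutral requirement, its unrelated-SAE sentence names the principal observation period, 7.2.1 requires all AEs over that period and the 24 weeks after it, and Table 3 schedules AE collection in Group B from baseline. The sentence about events before study medication gives pre-treatment examples (biopsies, washout, run-in), so it was plainly not meant to govern 72 weeks of control follow-up. For SAEs this reply stands. A reader might infer that Group B SAEs are limited to those caused by study procedures, and the documents do not support that. What remains is text giving two answers.

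A reader might also infer that laboratory AEs in Group B must be zero whatever happens. That fails too: serious laboratory values are reportable in any arm. Nor is an ALT flare alone an AE in either group, because it must meet one of the 7.1.3 conditions.

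The third inference is that the natural rate of ALT flares is lost. It is not. Laboratory results reach the database independently of the AE form, and SAP 4.6.3 summarizes graded values and ALT flares by treatment group.

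The reply is weaker on non-serious laboratory AEs. Section 7.2.1 requires AEs to be reported, but 7.1.3 is the specific rule for when a non-serious laboratory result becomes one, and it is tied to dosing. The general definition in 7.1.1 includes abnormal laboratory findings but is framed around a subject given a pharmaceutical product. Two careful sites could read these sections differently. Section 3.3 plans about 40 to 70 centers with a mean of 2 to 4 subjects each, in an open-label trial, so uniform reading cannot be assumed.

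**Conclusion.** The point holds in limited form. For non-serious laboratory AEs, Protocol 7.1.3 followed as written records the two randomized arms differently. This affects results that change concomitant therapy and the ALT/AST event with bilirubin or jaundice. For SAEs, 7.2.2 contradicts itself without excluding Group B.

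The exposure is confined to the AE and special-interest tables of the A-versus-B comparison. The primary efficacy analysis and the by-group laboratory summaries are untouched. The direction, if sites follow 7.1.3 literally, is to overstate the excess of AEs on PEG-IFN. The size cannot be computed: it depends on how often such events occur and on how many sites take the literal reading, and the documents give neither. The illustrative counts assume equal true rates and a literal reading at every site, which is the extreme case.

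The correction deserves to be made because the comparison is the primary safety analysis and the remedy is cheap. It will not equalize ascertainment altogether. Section 5.3 schedules 14 post-baseline visits to follow-up Week 24 in Group A (11 + 3) and 6 in Group B (4 + 2), which is a separate matter.

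**What to change.** In Protocol 7.1.3 and 7.2.2, state one anchor for both randomized arms, the baseline visit:
- Group A: first dose, which 5.3 places at the baseline visit.
- Group B: randomization/baseline.
- Group C and Switch treatment: first dose.

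In 7.1.3, replace treatment-emergent with post-baseline for Group B, so that the liver-injury event and the concomitant-therapy condition apply in both arms. In 7.2.2, restrict the sentence on events before study medication to the time between consent and randomization/baseline, and give the sentence on reporting after first study drug its Group B equivalent. Then check that both sections agree with 7.2.1.

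The cost is a few sentences in two protocol sections and a memo to sites. Group B's laboratory tests and AE collection are already scheduled, so no visit, sample or analysis is added.
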